Participants will be recruited from the Bariatric Surgery Programs at the Hospital of the University of Pennsylvania and Presbyterian Medical Center, all part of Penn Medicine. We will enroll participants until a total of 300 adults have completed baseline visits. We anticipate that we will need to consent a larger number of participants in order to meet this enrollment goal. Based on our previous studies of bariatric surgery patients, we expect that approximately 80% of participants will be women and 20% of participants will be ethnic minorities. [name], Director of the Bariatric Surgery Program, conducts approximately 300 bariatric surgery operations per year. Additional surgeons in the Bariatric Surgery Program (at the Hospital of the University of Pennsylvania, Presbyterian Medical Center, and Pennsylvania Hospital) operate on approximately 200 patients per year. In order to increase the diversity and size of our sample, participants will also be recruited from the Temple Health Bariatric Surgery Program. The patient flow at Temple Health is similar to that of the Penn Health System (described below). Participants will be approached by the Research team during their pre-operative testing and education process. The study team member who reviews the consent document will emphasize that participation in the study is voluntary and that medical care will not be influenced by the participants decision to participate or not.

Children and Adolescents not applicable

Adult Subjects Not Competent to Give Consent

Competence to provide informed consent will be assessed informally, as the likely degree of impairment in the population to be studied is minimal.

2. Waiver of Consent

Waiver or Alteration of Informed Consent* No Waiver Requested

Minimal Risk*

Impact on Subject Rights and Welfare*

Waiver Essential to Research*

Additional Information to Subjects

Written Statement of Research* No

If no written statement will be provided, please provide justificiation

The following documents are currently attached to this item:

There are no documents attached for this item.

Risk / Benefit

Potential Study Risks

Bariatric surgery poses several significant risks, including: gastric perforation, staple line disruption, disruption of the gastrojejunal anastomosis with a leak, deep vein thrombosis, pulmonary emboli, and death. These risks will be addressed with patients as part of their informed consent for surgery. Participation in the proposed study has no impact on the risks associated with surgery. WE NOTE THAT BARIATRIC SURGERY IS BEING PERFORMED INDEPENDENTLY OF THIS RESEARCH (I.E., SURGERY IS NOT A STUDY PROCEDURE). Patients overall physical health will be monitored by their bariatric surgeon and/or primary care physician. Thus, these professionals will be primarily responsible for monitoring patients health as they lose weight after surgery, including dietary intake and malnutrition, hypotension or hypoglycemia, or risks associated with increased physical activity. If these or other medical issues come to the attention of research study staff during a study visit, the patient will be encouraged to communicate these findings to his or her physician. The psychometric and more objective neurocognitive tests present little risk to participants. Similarly, the structured clinical interviews are believed to present little risk to participants. Finally, there is the potential that individuals connected with the study will see personal health information not relevant to the study. Risks of complications will be reduced by regularly monitoring participants progress. Safety reports will be created by the Research Coordinators and sent to the PIs and Data Safety and Monitoring Board (DSMB). Study staff will make clear that subjects are not obligated to participate in the study and that their answers will be held strictly confidential. Questionnaires will not contain any identifying information, thus, ensuring the confidentiality of subjects responses. Code numbers will be assigned to each subject to maximize anonymity when entering and analyzing data. All data collected will be received and kept in a locked filing cabinet and on a password-protected computer by the Research Coordinators. Subjects will be informed that they can withdraw from the study whenever they wish and that their withdrawal will not affect the medical care they receive.

Potential Study Benefits

Individual subjects may find participation in this study interesting, but will receive no health benefits from participating in this study. Results will provide important information on the changes in weight, psychopathology, disordered eating, and impulsivity associated with bariatric surgery.

Alternatives to Participation (optional)

The alternative is not to participate in the study.

Data and Safety Monitoring

Who will be responsible for monitoring? The Principal Investigators ([name]; Temple University), in conjunction with [name] (Site-Principal Investigator), the Penn research coordinator, and Temple University Project Director ([name], MSEd), will be responsible for overseeing and completing the monitoring process. How will monitoring be performed? During the course of the study, safety and data quality monitoring will be performed on an ongoing basis by the research coordinator, data manager, and study investigators. The Research Coordinator will be responsible for assembling the data and producing these reports, as well as assuring that all parties obtain copies of these reports. The PI, Co-Investigators, and Research Coordinator will meet weekly for approximately 60 minutes, where they will review patients safety and progress as they proceed through the study. Results of all assessments will be reviewed to determine whether subjects have experienced any adverse events. Any serious adverse events, although unlikely given the nature of the proposed study, will be reported within 24 hours to the universitys IRB. Weekly meetings will conclude with the identification of any steps that need to be taken to ensure patient safety. Study initiation. The project director, will be responsible for assuring that all staff and participants understand and accept the obligations incurred in undertaking this study in accordance with 21 CFR Parts 312, 511, 812, 813 and any other applicable regulations; the obligation to obtain informed consent in accordance with 21 CFR Part 50; the obligation to obtain IRB review and approval of a clinical investigation before the investigation may be initiated and to ensure continuing review of the study by the IRB in accordance with 21 CFR Part 56; and to keep the sponsor informed of such IRB approval and subsequent IRB actions concerning the study. Ongoing monitoring. Monitoring will be conducted in accordance with the University of Pennsylvania Sponsor-Investigator Standard Operating Procedure. Review of the rate of subject accrual and adherence to inclusion/exclusion criteria will occur monthly during the recruitment phase. A formal report will be created at the end of each recruitment wave of 80 enrolled participants (approximately 25%, 50% and 75% of subject enrollment) to assure that participants meet

eligibility criteria and ethnic diversity goals outlined in the grant proposal. Once participants have completed a baseline assessment, data on compliance to the protocol will be collected by research staff and reviewed by the study investigators, the study biostatistician, and the safety officer ([name], Department of Endocrinology and associated faculty at the Center for Weight and Eating Disorders at the Perelman School of Medicine at the University of Pennsylvania). Compliance will be reviewed with the semi-annual DSMP report (described below) and if the safety officer has concerns about whether compliance has reached a level that might inhibit the ability of the study to test its primary hypotheses, he/she will suggest a conference call for study investigators to discuss methods for improving compliance. In addition, the bariatric surgeons will inform the research team of any surgical or medical complications that occurred peri- or post-operatively among surgery patients. The research coordinator will file all meeting agenda and reports in the study regulatory binder. Assessing Adverse Events Definitions Unanticipated Problems Involving Risk to Subjects or Others Any incident, experience, or outcome that meets all of the following criteria: Unexpected in nature, severity, or frequency (i.e. not described in study-related documents such as the IRB-approved protocol or consent form, the investigators brochure, etc) Related or possibly related to participation in the research (i.e. possibly related means there is a reasonable possibility that the incident experience, or outcome may have been caused by the procedures involved in the research) Suggests that the research places subjects or others at greater risk of harm (including physical, psychological, economic, or social harm). Adverse Event An adverse event (AE) is any symptom, sign, illness or experience that develops or worsens in severity during the course of the study. Intercurrent illnesses or injuries should be regarded as adverse events. Abnormal results of diagnostic procedures are considered to be adverse events if the abnormality: results in study withdrawal is associated with a serious adverse event is associated with clinical signs or symptoms leads to additional treatment or to further diagnostic tests is considered by the investigator to be of clinical significance Serious Adverse Event Adverse events are classified as serious or non-serious. A serious adverse event is any AE that is: fatal life-threatening requires or prolongs hospital stay (not including expected hospitalizations related to bariatric surgery) results in persistent or significant disability or incapacity a congenital anomaly or birth defect an important medical event Important medical events are those that may not be immediately life threatening, but are clearly of major clinical significance. They may jeopardize the subject, and may require intervention to prevent one of the other serious outcomes noted above. For example, drug overdose or abuse, a seizure that did not result in in-patient hospitalization, or intensive treatment of bronchospasm in an emergency department would typically be considered serious. All adverse events that do not meet any of the criteria for serious should be regarded as non-serious adverse events. Adverse Event Reporting Period The study period during which adverse events must be reported is normally defined as the period from the initiation of any study procedures to the end of the study treatment follow-up. For this study, the study treatment follow-up is defined as at the 18month study assessment visit. Preexisting Condition A preexisting condition is one that is present at the start of the study. A preexisting condition should be recorded as an adverse event if the frequency, intensity, or the character of the condition worsens during the study period. General Physical Examination Findings At screening and baseline visits, any clinically significant abnormality should be recorded as a preexisting condition. At the end of the study, any new clinically significant findings/abnormalities that meet the definition of an adverse event will be recorded and documented as an adverse event. Abnormal Laboratory Values A clinical laboratory abnormality should be documented as an adverse event if any one of the following conditions is met: The laboratory abnormality is not otherwise refuted by a repeat test to confirm the abnormality The abnormality suggests a disease and/or organ toxicity The abnormality is of a degree that requires active management; e.g. change of dose, discontinuation of the drug, more frequent follow-up assessments, further diagnostic investigation, etc. Expected events Over the 24-month duration of the study, a number of medical events may be expected to occur in obese adults, including routine surgeries and procedures, the development of cancer or chronic conditions, new or increased symptoms from a chronic condition, musculoskeletal problems, and motor vehicle or other accidents (e.g., falls). We will record unexpected events which occur as a result of participation in this research study. The events will be reported to the DSMP but not the IRB. Monitoring for Adverse Events (AEs) and Serious Adverse Events SAEs) Surveillance for SAEs and other relevant clinical events that may be associated with study participation will occur at 6, 12, and 24 months. This will be done using an open-ended questionnaire which asks about new symptoms, urgent/unplanned medical care, and hospitalizations. All adverse events will be recorded but only related, unexpected, and serious events will be reported. Monitoring and Reporting: will be conducted in real-time by all study personnel who have direct contact with participants. Participants will also be instructed to contact the study physician, [name], should they experience any adverse events that occur due to participation to the research between study visits. Drs. [name] and [name] will review all the Adverse and Unexpected Event Case Report Forms. After removing identifying patient health information, any AE that is related AND unexpected will be reported to the University of Pennsylvania Institutional Review Board within 10 days. Serious adverse events (e.g., unexpected hospitalization see definition above) will be brought to the attention of the Investigators and study physician within 24 hours and reported in a timely fashion as required by the Data and Safety Monitoring Plan (DSMP), the IRB, and the NIH. If the serious adverse event involved a death that is unforeseen (unexpected) and indicates participants or others are at increased risk of harm, it will be reported to the IRB within 24 hours. For all other deaths the investigators will submit a report to the IRB within 3 days. Data, safety and monitoring report. The PIs will provide a summary of the DSMP report to the NIH on an annual basis, as part of the progress report. The DSMP report will include the participants sociodemographic characteristics, expected versus actual recruitment rates, retention rates, any quality assurance or regulatory issues that occurred during the past year, summaries of AEs and SAEs, and any actions or changes with respect to the protocol. The DSMP report to NIH will also include, if applicable, the results of any hypothesis-testing data analysis conducted. External review. To ensure that the investigators employ appropriate data and safety monitoring strategies, we will have two external reviewers to monitor the study. [name] (assistant professor of psychiatry and human behavior at The Warren Alpert Medical School of Brown University and The Miriam Hospital) will be asked to review participant recruitment, retention, and statistical power. [name]. (a physician at Temple University) will be asked to review reports of adverse events in the surgicallytreated patients. In each case, reviewers will receive semi-annual summaries of our findings, following enrollment of the first participant. One of these two reports will coincide with the annual DSMP report. Reviewers will provide their evaluation and recommendations during regularly-scheduled telephone conference calls. Evidence of training in human subject research. All research personnel associated with this study will have completed the University of Pennsylvanias Collaborative Institutional Training Initiative (CITI) for patient oriented research, as well as HIPAA Compliance Training. Documentation of this training will be retained in the study regulatory binder.

The following documents are currently attached to this item:

There are no documents attached for this item.

Risk / Benefit Assessment

The benefits of this research far surpass the risks. Results will provide important information on weight loss, dietary intake, eating behavior, and physical activity in patients who have undergone bariatric surgery. As noted above, bariatric surgery entails significant risks. Subjects in the proposed study are presenting for surgery of their own volition and are not being randomly assigned to surgical treatment. The risks inherent in bariatric surgery are not affected by participation in the proposed study. The knowledge gained from this study could potentially advance the management of individuals who undergo bariatric surgery.

General Attachments

The following documents are currently attached to this item:

There are no documents attached for this item.

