****NOTE: THE SURGICAL WEIGHT LOSS INTERVENTION IS NOT A STUDY PROCEDURE. PARTICIPANTS WILL HAVE ALREADY DECIDED TO SEEK SURGERY PRIOR TO THE RESEARCH BEING PRESENTED TO THEM**** Participants will complete the following assessments at baseline, and 6, 12, and 24 months after surgery. The measures that will be used at each assessment are described below: Impulsivity: Impulsivity measures will be administered via study laptops in a quiet laboratory testing room at the following time points: baseline and 6, 12, and 24 months after surgery. All tasks are programmed in E-Prime 2.0 (Psychology Software Tools, Inc.). Total administration time is approximately 25 minutes. The tasks are: Stop Signal Task (SST)117: measure of response inhibition which has been used in previous studies of smoking behavior118-120 and obesity.71,72 In this task, participants respond to left and right-facing arrows (go signal) on the computer screen. On 25% of trials, a stop signal (an 800-Hz, 100-ms, 70-dB tone) is presented indicating that the participant should inhibit a response. The initial stop delay in each block is 250ms and adjusts ±50ms depending on whether the participant successfully inhibits.117 Participants complete three 64-trial task blocks. Trials consist of a 500-ms warning stimulus, a 1,000-ms go signal, and 1,000ms blank screen inter-trial interval. Task duration is approximately 10 min. The primary outcome is stop signal reaction time (SSRT), calculated as the mean RT on go-trials (MRT) minus mean stop delay (MSD). Stroop Test: measure of interference control, or the ability to suppress habitual responses.121 Higher Stroop interference scores are associated with obesity122,123 and disinhibition as assessed by this subscale of the Eating Inventory.124 Participants view a series of words on a computer monitor and using the keyboard, are asked to press the key associated with the color of the word rather than the word itself. Congruent trials are trials in which the word and color match (e.g., the word green appears in the color green). Incongruent trials are trials in which, the words are printed in colors that do not match the colors of the words (e.g., the word "red" might appear in green). Correct responses and reaction time (RT) for congruent and incongruent trials are recorded. The primary outcome is the interference score, which is also calculated as RT(incongruent) minus RT(congruent) and measures the ability to suppress a habitual response in favor of an unusual one, taking into account overall speed of naming. Delay

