
Discounting Task (DDT): participants choose between a smaller reward available immediately (e.g., \$20 today) and a larger reward available after a longer delay (e.g., \$40 in a month). People differ in their degree of delay discounting, the extent to which they forgo larger monetary magnitudes in the future in order to obtain immediate rewards. As in previous work, the immediate reward will be fixed and the magnitude and delay of the larger, later reward will vary from trial to trial. Participants will make 51 choices. The primary outcome will be the subjects discount rate, which will be estimated by fitting a logistic regression that assumes a persons decisions are a stochastic function of the difference in subjective value between the two options.127 Keeping with standard behavioral findings128,129 we will assume that subjective value (SV) is a hyperbolic function of the reward amount (A) and delay (D): SV = A/(1+kD), where k is the participants discount rate. Larger values of k indicate a greater degree of discounting future rewards. A composite measure of impulsivity will be calculated by averaging individual z-scores derived from the SST, Stroop interference score, and k-value. We predict that higher levels of impulsivity indicating poor response inhibition and greater discounting of future rewards (i.e., slower SST, higher Stroop interference score, and higher k-values) will be associated with less weight loss 24 months following bariatric surgery. Psychopathology: Psychopathology measures will be administered via interview or questionnaire at the following time points: baseline and 6, 12, and 24 months after surgery. The tasks are: Structured Clinical Interview for the DSM-5, Research Version (SCID-5-RV)129 is a semistructured interview for making DSM-5 diagnoses for mood, anxiety, eating, substance use, and psychotic disorders. A trained clinician or mental health professional who is familiar with the DSM-5 classification and diagnostic criteria administers the measure, which takes about 2.5 hours. Beck Depression Inventory-II (BDI-II)130: survey used to measure mood. It is the most widelyused measure of depressive symptomatology. Alcohol Use Disorders Identification Test (AUDIT)164: assesses the presence of alcohol use disorders before and after surgery. The Drinker Inventory of Consequences131 is a self-administered 50-item questionnaire designed to measure adverse consequences of alcohol use in five areas: Interpersonal, Physical, Social, Impulsive, and Intrapersonal. Each scale provides a lifetime and past 3-month measure of adverse consequences, and scales can be combined to assess total adverse consequences. The Fagerström Nicotine Tolerance Questionnaire132 is an 8-item, self-report designed to measure physical dependence to nicotine. Urine Drug Screens: collected in temperature sensing cups to ensure valid samples. Urines will be tested for common drugs of abuse (cocaine, opiates, amphetamines, methamphetamine, marijuana). A composite measure of psychopathology will be calculated by averaging individual z-scores derived from the presence/absence of DSM diagnoses, the BDI-II score, and the substance use measures. We predict that higher levels of psychopathology will be associated with less weight loss 24 months following bariatric surgery. Eating Behavior: Eating behavior measures will be administered via interview or questionnaire at the following time points: baseline and 6, 12, and 24 months after surgery. Total administration time is approximately 30 minutes. The tasks are: The Eating Inventory134: 51-item self-report inventory that measures three factors related to eating behavior: 1) cognitive restraint, 2) disinhibition, and 3) hunger. Eating Disorders Examination-Bariatric Surgery Version135: Identical to the widely-used Eating Disorders Examination but also measures eating disturbances specific to bariatric surgery by adding specific questions regarding dumping, plugging, chewing and spitting, and vomiting. (Note. The diagnosis of BED will be established from the SCID interview. The results of the EDE-BSV will be used as a continuous variable in the analyses described below.) Night Eating Questionnaire (NEQ)127: 14-item scale that measures symptoms of night eating and has been used in bariatric populations previously. Yale Food Addictions Scale136: 25-item mixed response scale that is used to identify those who are using high sugar/high fat foods in ways similar to symptoms that are markers of substance use, such as tolerance, withdrawal, and loss of control. A composite measure of disordered eating will be calculated by averaging individual z-scores derived from these measures. We predict that higher levels of disordered eating will be associated with less weight loss 24 months following bariatric surgery. Weight: Weight will be measured with a calibrated digital scale with subjects dressed in light clothing and without shoes. Percent weight loss will be calculated from participants current weight (at each assessment point) as compared to their baseline weight. Participants with higher levels of impulsivity, psychopathology, and disordered eating are predicted to lose less weight at 24 months as compared to those with lower levels. Psychosocial Status: Medical Outcomes Study 36-Item Short Form Survey (SF-36)137: used to measure quality of life Impact of Weight on Quality of Life-Lite (IWOOL-Lite) 138: used to measure quality of life Dietary Intake: ASA-24: public-access, freely available (through the National Cancer Institute), web-based tool to obtain high-quality dietary intake data with minimal bias, making it a preferred tool for studying diet and disease associations.139 These 24-hour food recalls will be conducted at each time point for one weekday and one weekend day. Physical Activity: College Alumnus Survey (commonly known as the Paffenbarger Survey140): calculate self-reported leisure time physical activity kilocaloric expenditure per week. The frame of reference will be the past 6

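### SSRT is scored as mean go RT minus mean stop delay although the stop-delay staircase restarts at 250 ms in every block, so the impulsivity score partly measures general response speed

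*Combined protocol and SAP*

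**What the plan says.** The task is described under Study Procedures, and in the same terms under Study Instruments.

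- Trials: "Participants complete three 64-trial task blocks". "On 25% of trials, a stop signal" is given, which makes about 16 stop trials per block.
- Staircase: "The initial stop delay in each block is 250ms and adjusts ±50ms depending on whether the participant successfully inhibits".
- Timing: each trial includes "a 1,000-ms go signal".
- Score: SSRT is "calculated as the mean RT on go-trials (MRT) minus mean stop delay (MSD".
- Direction: the impulsive pattern is described as "slower SST, higher Stroop interference score, and higher k-values".
- Composite: "A composite measure of impulsivity will be calculated by averaging individual z-scores derived from the SST, Stroop interference score, and k-value".

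Under Overall objectives, Specific Aim 1, on which the study is powered, tests the individual measures. The Analysis Plan splits each baseline measure into Low and High (Hypothesis 1) and does the same for the change from baseline to 6 months (Hypothesis 2).

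No section leaves out ramp-up stop trials, requires or reports an inhibition rate near 50%, or lists go RT as a covariate. The planned data screening is generic: outliers, missing data and normality. The one mention of flagging behavioral performance sits in the text on image quality.

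**The concern.** Subtracting the mean stop delay from the mean go RT recovers SSRT if the staircase hovers around the delay at which half of the stops succeed. That delay is roughly go RT minus SSRT. Here each block starts at 250 ms whatever the participant's speed. A participant whose balance point is 450 ms needs four upward steps to reach it, three times over, and every one of those trials enters the mean delay.

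The resulting error depends on how fast a person responds, not on how well the person inhibits. It does not cancel on z-scoring, because it differs between people. What is at stake is the SSRT predictor in the primary aim, its third of the composite, and the 6-month change in SSRT if overall speed changes after surgery.

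**Working it through.** The plan states no SSRT value, inhibition rate or reliability, so there is no figure of its own to reproduce.

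**Inputs from the plan.** Stop trials per block: 0.25 × 64 = 16; in total 3 × 16 = 48. Start 250 ms in each block; step 50 ms.

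**Assumptions (not in the plan).** The delay rises after a successful stop and falls after a failed one, which is the usual reading. True SSRT is 250 ms with a trial SD of 30 ms. Go RT is either normal (SD 100) or right-skewed (normal SD 80 plus exponential 80), with and without a 1,000-ms response limit.

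**Step 1: ramp by hand.** Steps to balance: k = (go RT − SSRT − 250)/50. Shortfall in mean stop delay = 50 × (1 + … + k)/16.

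- Go RT 600: k = 2; 50 × 3/16 = 9.4 ms.
- Go RT 700: k = 4; 50 × 10/16 = 31.2 ms.
- Go RT 800: k = 6; 50 × 21/16 = 65.6 ms.
- Go RT 500: k = 0; no error. Go RT 400: k = −2; −9.4 ms.

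A block that ends k steps above its start has about (16 + k)/2 successful stops. That is 7/16 = 0.44 at go RT 400, 10/16 = 0.625 at 700 and 11/16 = 0.69 at 800. The 50% condition therefore fails in step with go speed.

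**Step 2: race-model simulation of the stated task.** Bias in ms, range over the assumption sets:

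| Mean go RT | As planned | Integration, all stop trials | Mean method, first 8 stop trials per block dropped |
|---|---|---|---|
| 400 | −19 to −15 | −8 to −3 | −2 to +5 |
| 500 | 0 to +6 | −4 to 0 | −1 to +7 |
| 600 | +19 to +25 | −1 to +3 | +1 to +9 |
| 700 | +43 to +49 | +8 to +12 | +3 to +11 |
| 800 | +68 to +82 | +25 to +29 | +1 to +16 |

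Right-skewed go RTs generally add a few ms to the planned score. The restart is the main driver: with one staircase carried across blocks, the bias at 700 ms falls to +14 to +21 ms.

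**Step 3: populations in which true SSRT is independent of go RT.**

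With SSRT SD 40, go RT SD about 100 and mean go RT about 500-700 ms:
- Correlation with true SSRT is about 0.68-0.82 as planned and 0.79-0.89 by integration.
- Correlation with go RT, which should be zero, is about 0.41-0.61 as planned and 0.14-0.42 by integration.
- In one such run the ranges with true SSRT were 0.71-0.82 and 0.81-0.89. Squared ratios: (0.82/0.89)² = 0.85 and (0.71/0.81)² = 0.77. The planned score gives up about 15-23% of the explainable variance relative to integration.

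With SSRT SD 30 or 50, go RT SD 80-100 and mean go RT 550-650 ms:

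| | As planned | Integration | First 8 dropped, mean method |
|---|---|---|---|
| Correlation with true SSRT | 0.62-0.85 | 0.75-0.91 | 0.76-0.89 |
| Correlation with go RT | 0.34-0.61 | 0.08-0.29 | 0.00-0.02 |
| Low/High misclassified | 17-29% | 13-23% | 15-23% |

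As planned, the slowest quarter is labelled High 68-86% of the time and the fastest quarter 20-33%; 50% is expected for each.

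**Step 4: change scores.** A general speed-up of 50 ms with unchanged SSRT gives a false SSRT improvement of 10-11 ms by the planned score and 4-8 ms by integration.

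**The case against.** The best defence is that the size of the problem is assumed. The plan gives no go RT, SSRT or between-person SD. The largest errors need slow responding against a 1,000-ms go signal, and nothing shows that this cohort is that slow. This stands, and the figures should be read as illustrative.

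The effect on the composite is also modest. If the Stroop score and k are independent, equally weighted and measured without error, the correlation with the true composite is 0.92-0.94 by the mean method and 0.95-0.97 by integration (mean go RT 500-600 ms). SSRT is one of many individual predictors, and part of its error is sampling noise from only 48 stop trials, which no rescoring removes. The staircase is cited to a source not seen here.

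A reader might infer more than the documents support in three ways:

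- *That anyone far from the starting delay is scored as too impulsive, in proportion to go RT.* The error reverses for fast responders, is near zero around a 250-ms difference, and grows faster than linearly above it.
- *That most of each block is spent climbing.* At go RT 700 and SSRT 250 the ramp is four steps out of 16 stop trials.
- *That the impulsivity effect is confounded.* This needs go speed to be related to weight loss within the cohort. The Background reports motor-speed deficits in surgical candidates and links metabolic dysregulation to cognitive deficits, but it does not link speed to weight loss after surgery.

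None of this removes the core point. The direction of the error follows from the stated start, step and block length on the usual staircase reading, and it held under every assumption set tried.

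**Conclusion.** The scoring rule does not suit the task as described. It ties SSRT to general response speed: upward for participants whose go RT exceeds true SSRT by well over 250 ms, downward for those well under it. The consequence that can be defended is dilution of a primary-aim predictor and of one third of the composite. Confounding remains a possibility only.

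The size rests on assumed RT distributions, on the usual up-after-success staircase and on true SSRT being independent of go RT. Under those assumptions the loss is worth correcting, because the change is cheap and integration gave a higher correlation with true SSRT in every population examined. It is a scoring correction to one predictor, not a flaw that invalidates the aim.

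**What to change.** Keep the task unchanged and replace the scoring rule before analysis:

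1. Leave the early ramp-up stop trials of each block out of the estimate, for example the first 8.
2. Score the rest by the integration method: the go RT at the percentile equal to the observed probability of responding on those stop trials, minus their mean stop delay.
3. Report each participant's achieved inhibition rate.
4. Keep mean go RT minus mean stop delay as a sensitivity analysis, with go RT as a covariate.

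Both elements are needed. Integration on all stop trials still leaves a link with go speed (about 0.14-0.42 or 0.08-0.29 in the two sets of populations above). Dropping early trials removes that link almost entirely, and integration deals with any remaining departure from 50% inhibition and with skewed go RTs.

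The cost is some rescoring, with no added patient burden. It depends on trial-level task data being retained, which the documents do not state for this task. Fewer stop trials also enter each estimate: 3 × 8 = 24 instead of 48. The combined score is therefore somewhat noisier than integration on all trials, and the number dropped should be fixed in advance with that trade-off in view.
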